The primary efficacy endpoint is the percent change (PCH_T) in the frequency (unweighted score) of IA behaviors per 7 days in the Treatment Phase (titration + maintenance) relative to the Baseline period calculated over the number of days with non-missing IA diary data.

The primary efficacy endpoint PCH_T will be calculated by $PCH_T = 100^*(T - B)/B$, where T and B are IA behavior frequencies per 7 days during the Treatment Phase and Baseline period, respectively. The IA behavior frequency per 7 days is defined as (SUM/DAY) x 7, where SUM is the total of the 15 IA behaviors reported in IA diary, and DAY is the number of days with non-missing IA score in the IA diary during the specified study period.

Key Secondary Efficacy Endpoints:

- 1. Investigator-rated CGI-S scale
- 2. R-MOAS rating scale
- 3. R-MOAS remission rate defined by a score ≤ 10

Additional Secondary Endpoints:

- 1. Investigator-rated CGI-I scale
- 2. Caregiver-rated CGI-I scale
- 3. Caregiver-rated CGI-S scale
- 4. SNAP-IV rating scale
- 5. CHQ-PF28 rating scale
- 6. SIPA rating scale

Additional Secondary Safety and Tolerability Endpoints:

- 1. Incidence of Adverse Events
- 2. Incidence of Extrapyramidal Symptoms (EPS) as assessed by Simpson-Angus Scale Barnes Akathisia Scale, Abnormal Involuntary Movement Scale
- 3. Columbia Suicide Severity Rating Scale (C-SSRS)
- 4. Laboratory Parameters (Hematology, Chemistry, Urinalysis, Insulin and Prolactin)
- 5. Vital signs, Standardized BMI, Physical Examination and ECG (12-lead)
- 6. Infrequent Behaviors Checklist

Exploratory Endpoints:

1. IA Diary Cross-Validation

The data generated from 810P301 and 810P302 pediatric studies during the diary validation process may be used for cross-validation of the IA Diary in adolescents. If the decision is made to proceed with the analysis, the cross-validation plan and results will be provided in a separate stand-alone report.

This document is confidential. It contains proprietary information of Supernus[®] Pharmaceuticals, Inc. Any viewing or disclosure of such information that is not authorized in writing by the Sponsor is strictly prohibited. Such information may be used solely for the purpose of reviewing or performing this study.

2. Population Pharmacokinetics/Pharmacodynamics:

3. Pharmacogenomics (PGx) Testing:

Pharmacogenomic testing is optional. The DNA will be extracted and tested for any genetic variations associated with CYP2D6 enzyme. This enzyme is involved in the metabolism of molindone and genetic variations of the CYP2D6 gene may affect the pharmacokinetics of the drug. Test results in this study will identify the subject's metabolizer phenotype.

Sample size:

Assuming a mean difference of 15 between SPN-810 dose group and placebo with a common standard deviation of 35, a sample of 93 subjects per arm will yield 80 % power to detect a non-zero difference between the median of SPN-810 treatment group and the placebo group using the Wilcoxon rank-sum test with a 2-sided significance level α =0.05.

It is assumed that approximately 20% subjects will dropout before the completion of the study and hence, an adjusted total of 186 subjects will be randomized in a 1:1 ratio to obtain approximately 150 subjects at the completion of the study.

Sample size may be recalculated based on the effect size of the ongoing 810P301 and 810P302 studies.

Analysis Populations:

Safety Population: will include all subjects who received at least 1 dose of study drug and had at least one post-baseline safety assessment.

FAS (Full Analysis Set): include all subjects who received at least 1 dose of study drug and have completed baseline and at least 1 valid post-randomization assessment of frequency of IA behaviors based on IA diary entry.

Per-Protocol (PP) Population: will include all of the subjects who completed the Treatment Phase and did not have major protocol deviations (as defined in the SAP).

PK population: will include all subjects in the safety population who have received at least 1 dose of active study medication and had one PK sample drawn which had quantifiable concentration for molindone.

Efficacy Hypothesis:

Let μ_1 , and μ_2 represent the median percent change in the frequency of IA behaviors per 7 days in the Treatment Phase relative to the Baseline period in the FAS population for subjects treated with placebo and SPN-810 treatment, respectively. The null (H₀) and the alternative (H_a) hypotheses are as in the following:

 $H_0: \mu_2 = \mu_1$, [there is no difference between the median of the SPN-810 treatment group and the median of placebo group] vs. $H_a: \mu_2 \neq \mu_1$, [there is a difference between the median of the SPN-810 treatment group and the median of placebo].

Handling Missing Data:

For the efficacy endpoint, the frequency of IA behaviors during the Treatment Phase will be calculated over the number of days with non-missing IA diary data in the Treatment Phase (titration + maintenance).

For subjects who have partial IA diary data during Maintenance period (<7 days with nonmissing IA diary data), the IA behaviors from both Titration and partial Maintenance period will be counted together and used for the Maintenance period. For subjects with IA diary data only available during Titration period, the IA behaviors from the Titration period will be used for the Maintenance period.

Statistical Methods:

Summaries for continuous variables will include the sample size, mean, and standard deviation, median, minimum, and maximum. Summaries for discrete variables will include the tabulation of frequencies and percentages.

Analysis of PCH_T will be performed using the Wilcoxon rank-sum test to test the hypothesis of equality of the median of SPN-810 treatment group with the median of the placebo group. The Hodges-Lehmann estimate and the associated 95% confidence interval (CI) will be calculated.

Each of the secondary endpoints will be analyzed using a Mixed-Effect Model for Repeated Measure (MMRM). MMRM assumes missing data as Missing at Random. The model includes treatment, visit, and interaction between treatment and visit as fixed factors, baseline as covariate. The model parameters will be estimated using restricted maximum likelihood method with unstructured variance-covariance matrix and Kenward-Roger approximation to estimate denominator degrees of freedom. The between-group comparison will be performed using the simple contrast at the respective visits.

The least squares mean of the treatment groups, the difference in the least squares mean (SPN-810 minus placebo), and the 2-sided 95% CI for the difference will be obtained.

Safety Monitoring:

An independent and unblinded Data and Safety Committee (DSC) will be established to assess the safety of the subjects participating in the study. An interim safety data analysis will be performed if required to support a registration filing. The DSC will consist of 3 individuals.

Safety Analysis:

Safety analyses will be based on the safety population. All AEs will be coded using the Medical Dictionary for Regulatory Activities (MedDRA) and preferred term. All AEs with onset date on or after the first dose of double-blind study medication and prior to 7 days after the permanent discontinuation of study medication (onset date – last date of dose <=7) will be summarized using discrete summaries at the subject and event level by system organ class and preferred term for each treatment group. AEs with onset date after Visit 7, will be summarized in the OLE study (810P304) for subjects who decide to enroll in the OLE. Similarly, treatment-emergent AEs will be summarized by severity and relationship separately. Vital signs and all other safety endpoints will be summarized using descriptive statistics by treatment groups. If applicable, categorical laboratory tests will be summarized using number and percent of subjects by treatment groups. Data on infrequent behaviors will be listed.

IA Diary Cross-Validation:

Cross-validation model generated based on the results from the validation of the IA diary in the 810P301 and 810P302 studies may be used to predict and estimate the accuracy of electronic IA diary to measure aggressive behaviors in adolescents.

Pharmacokinetic Analysis:

Bioanalytical Analysis:

Pharmacogenomics (PGx) Analysis:

The DNA will be extracted and tested for any genetic variations associated with CYP2D6 enzyme. The residual DNA will be stored for possible testing of genes involved in the efficacy and possible association with particular adverse events of the drug (e.g., understand the nonresponders to treatment and/or individuals who show unusual safety profile). The DNA analysis will not be used for individual genetic characterization and the subject identity will be kept confidential. The PGx report will be a stand-alone document.

TITLE F	PAGE	
SUPER	NUS PH	IARMACEUTICALS, INC. PROTOCOL APPROVAL PAGE
SUMM	IARY OF	CHANGES4
CLINIC	AL PRO	TOCOL SYNOPSIS
LIST O	F TABLE	S AND FIGURES
	F ABBRI	EVIATIONS
1.	ETHICS	5
	1.1	Institutional Review Boards / Independent Ethics Committees
	1.2	Ethical Conduct of the Study
	1.3	Investigators and Study Personnel
	1.4	Subject Information and Consent/Assent
2.	INTRO	DUCTION
	2.1	Background
	2.2	Impulsive Aggression Comorbid with ADHD
	2.3	Current Treatment Options
	2.4	Sponsor's Phase 2 Studies
	2.5	Sponsor's Phase 3 Studies
	2.6	IA Diary
	2.7	Study Rationale
3.	STUDY	OBJECTIVES
	3.1	Primary Objective

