4.3.2 Treatment Phase: (2-5 weeks)

4.3.2.1 Titration period (2 weeks), Day 1 to Day 14

Inclusion/exclusion criteria will be re-assessed to verify eligibility prior to study randomization at the end of Visit 3. Eligible subjects will be randomized at Visit 3 (Day 1) in a 1: 1 ratio to receive 36 mg/day SPN-810 or placebo and proceed to the two-week Titration period in order to reach the maintenance dose of 36 mg/day over a period of 2 weeks.

4.3.2.2 Flexible Maintenance period (3 weeks), Day 15 to Day 35

Following dose titration, all subjects will remain at the reached dose of SPN-810 (36 mg/day) or placebo on the first week of the Maintenance period. After the first week, the Investigator will clinically assess whether to increase the dose to 45 mg/day SPN-810 or placebo, or remain at 36 mg/day of SPN-810 or placebo. On the following week, the Investigator will re-assess the dosage: the subject may remain at 36 mg/day or 45 mg/day or matching placebo (depending on the dosage from the previous week) or titrate up to the higher dose of 45 mg/day or 54 mg/day of SPN-810 or placebo, respectively. Dose reduction will also be allowed during the second week of the Maintenance period in consultation with the Medical Monitor and the Sponsor; at Visit 6 the Investigator may adjust the dose based upon tolerability.

4.3.3 Conversion Phase (10 days), Day 36 to day 45

At the end of the 3-week Maintenance period (Visit 7), subjects will enter a 10 day Conversion Phase if the subject chooses to enroll into an ongoing open-label extension (OLE) study (i.e., 810P304). A blinded double-dummy conversion card will be distributed to down or up-titrate

This document is confidential. It contains proprietary information of Supernus[®] Pharmaceuticals, Inc. Any viewing or disclosure of such information that is not authorized in writing by the Sponsor is strictly prohibited. Such information may be used solely for the purpose of reviewing or performing this study.

CONFIDENTIAL Version 3

the study medication and matching placebo. Subjects will return to the study site for a final end-of-study (EOS) visit, (Visit 8), after completing the Conversion Phase (Figure 1).

4.3.4 Taper Phase (10 days), Day 36 to day 45

At Visit 7, subjects who opt to discontinue from the study will receive a blinded taper card to titrate down the study medication. At the completion of the Taper Phase, subjects will return to the study site to complete the EOS procedures (Figure 2).

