- 8. Collect blood samples for hematology and chemistry
- 9. Administer Columbia Suicide Severity Rating Scale (C-SSRS)
- 10. Administer Caregiver and Investigator-completed CGI-S scale
- 11. Administer Caregiver and Investigator-completed CGI-I scale
- 12. Administer SNAP-IV, CHQ-PF 28 and SIPA scales
- 13. Administer safety scales (Simpson-Angus, Barnes-Akathisia, AIMS)
- 14. Record adverse events
- 15. Record Infrequent IA Behaviors
- 16. Record concomitant medications
- 17. Collect returned SM; assess treatment compliance
- 18. Dispense SM (either taper or conversion card based upon the subject's decision about participation in the open-label extension)

5.3.8 Visit 8/ End of the Study, Day 46

Visit 8 will occur 10 days (±1 day) following Visit 7 according to the Schedule of Visits and Procedures. These procedures will be performed for all subjects who complete the Maintenance period and for those who discontinue early. Subjects who discontinue after Visit 4 will be offered a taper kit and return to the study site to complete Visit 8. Any subject, who discontinues between Visit 3 and Visit 4, will be instructed to return to the study site for the final visit, within one week after discontinuation.

- 1. Administer R-MOAS scale
- 2. Record vital signs (HR, BP, temperature, and RR)
- 3. Record height, weight and BMI
- 4. Collect blood for hematology and chemistry
- 5. Collect urine for urinalysis, drug screen and pregnancy test
- 6. Administer Columbia Suicide Severity Rating Scale (C-SSRS)
- 7. Administer safety scales (Simpson-Angus, Barnes-Akathisia, AIMS)

- 8. Record adverse events
- 9. Record concomitant medications
- 10. Collect SM and assess treatment compliance
- 11. Collect Diary
- 12. Complete/Discontinue subject

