6.4.2.2 Recording and Evaluation of Adverse Events

All subjects who provided written Informed Consent (starting at Visit 1) will be questioned regarding the occurrence of AEs. Treatment emergent adverse events (TEAE) are undesirable events not present prior to study treatment/procedure, or an already present event that worsens either in intensity or frequency following the study treatment/procedure. A treatment emergent adverse event (TEAE) is an adverse event that

This document is confidential. It contains proprietary information of Supernus[®] Pharmaceuticals, Inc. Any viewing or disclosure of such information that is not authorized in writing by the Sponsor is strictly prohibited. Such information may be used solely for the purpose of reviewing or performing this study.

CONFIDENTIAL Version 3

Page 68 of 180

occurs after study treatment/procedure has started. TEAEs occurring prior to the administration of the study medication (Day 1) will become part of the subject's medical history including the severity of the event. At each visit, the Investigator must seek information on AEs by specific questioning and, as appropriate, by examination. Information on all AEs should be recorded immediately in the source document and also in the appropriate AE module of the eCRF. All clearly related signs, symptoms, and abnormal diagnostic procedures/laboratory results should be recorded in the source document, though they may be assessed as one diagnosis. For example fever, elevated white blood cells, cough, abnormal chest X-ray, etc., may all be reported as pneumonia.

All AEs occurring after enrollment and throughout the study period must be recorded. A treatment-emergent adverse event (TEAE) is defined as an AE with a start date on or after the first dose of study drug, or that worsened following first administration of study drug. For subjects who receive SM, TEAEs will be collected starting from the first dose of SM. The clinical course of each AE should be followed until resolution or until, in the medical judgment of the Investigator, the event has stabilized or is assessed as chronic.

For subjects who opt to enroll in the OLE (810P304) study, occurrence of AEs will be assessed starting at Visit 8 of this study (810P503) or Visit 1 in the OLE. AEs occurred in this double-blind study or ongoing after Visit 7, will be part of the medical history in the OLE study.

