9.5.1 Adverse Events

AEs will be classified into standardized medical terminology from the verbatim description (Investigator term) using the Medical Dictionary for Regulatory Activities (MedDRA). AEs will be summarized using discrete summaries at the subject and event level by system organ class and preferred term for each group of doses. Similarly, treatment-emergent AEs will be summarized by severity and relationship separately. Verbatim description and all MedDRA level terms, including the lower level terms, for all AEs will be contained in the subject data listings.

All AEs occurring throughout the study period will be recorded. Treatment-emergent AEs (TEAEs) will be collected starting after the first dose of study medication (after Visit 3) to the end of the study. These AEs include those that emerge during treatment or worsen in severity during treatment. These AEs will be tabulated, listed, and analyzed.

Separate TEAE incidence tables will be presented for the two treatment groups. The incidence rates for all SADRs will also be summarized as described for all TEAEs.

In addition, these same tables will be presented by treatment period (Titration, Maintenance, and combined Titration and Maintenance). For the combined Titration and Maintenance Periods, the incidence of TEAEs will also be presented by highest severity reported and the dose of SM at first occurrence. Listings (and tabular summaries, if warranted) of deaths, other SAEs, and other significant TEAEs, including TEAEs resulting in treatment discontinuation, will be provided.

9.5.2 **C-SSRS**

C-SSRS outcomes will be summarized using number and percent of subjects by categories for suicidal ideation only, suicidal behavior only and suicidality (ideation and behavior combined). The summary will be presented by treatment group. The proportion of subjects in each treatment group will be compared with the proportion of subjects in the placebo group using Fisher's exact test or Chi-square test as applicable if appropriate.

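### For extension enrollees, AEs starting between Visit 7 and Visit 8 have no consistent home: they may be missing from both studies' summary tables, or be counted as placebo events after placebo subjects appear to start active drug

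*Protocol*

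**What the plan says.** The rule for extension enrollees is in the Safety Analysis paragraph of the protocol synopsis: "AEs with onset date after Visit 7, will be summarized in the OLE study (810P304"). The sentence before it sets the general window for this study's AE summary, from the first double-blind dose to 7 days after study medication is permanently stopped.

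Protocol 6.4.2.2 says of the same subjects that "occurrence of AEs will be assessed starting at Visit 8 of this study (810P503) or Visit 1 in the OLE", and then that "AEs occurred in this double-blind study or ongoing after Visit 7, will be part of the medical history in the OLE study".

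Protocol 9.5.1 says that TEAEs "will be collected starting after the first dose of study medication (after Visit 3) to the end of the study". It makes no exception for extension enrollees. Its by-period TEAE tables cover titration, maintenance and the two combined.

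The interval in question is the one headed "Conversion Phase (10 days), Day 36 to day 45" in protocol 4.3.3. Protocol 5.3.8 fixes its end: "Visit 8 will occur 10 days (±1 day) following Visit 7 according to the Schedule of Visits and Procedures".

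Protocol 8.1 lets the SAP supersede the protocol's statistical methods. SAP 7.1.1 plans TEAE incidence by system organ class, preferred term and severity, with no onset window and no mention of extension enrollees. SAP 5.1 presents results in two groups, Placebo and SPN-810. The exposure categories in SAP 5.6 stop at Week 5.

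**The concern.** The synopsis moves an AE that starts during conversion out of this study's summary. Section 6.4.2.2 places the same AE before AE assessment begins for the OLE and treats it as history there. Section 9.5.1 would keep it here. The SAP, which should decide, does not.

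The interval matters because treatment changes in it. Protocol 4.2 says that a blinded double-dummy card adjusts the total daily dose to 36 mg for entry into the extension. The synopsis and 4.3.3 say that the card can move the dose down or up. For a placebo subject this appears to be the first active exposure. At stake are the tabulation of AEs from that exposure and the between-arm safety comparison. Safety is one of the few analyses that SAP 5.1 keeps.

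**Working it through.** The plan states no figure to reproduce, so the check is mainly a reading of the texts side by side.

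**1. Length of the interval.** Days 36 to 45 (protocol 4.3.3): 45 − 36 + 1 = 10 days. Titration and maintenance run from Day 1 to Day 35 (4.3.2.1, 4.3.2.2), so an extension enrollee has 35 + 10 = 45 dosed days, and 10/45 = 22% of them fall in the interval.

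**2. Which study the interval belongs to.** Visit 8 (Day 46) is the end-of-study visit of 810P503 (4.3.5, 5.3.8), and 5.4.9 keeps the blind to the end of Conversion/Taper. Days 36 to 45 are therefore part of 810P503.

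**3. One AE with onset on Day 40 in an extension enrollee.**

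- Synopsis: the 7-day limit runs from permanent discontinuation, and this subject has not discontinued. The next sentence applies and assigns the AE to 810P304.
- Protocol 6.4.2.2: Day 40 is before Visit 8. The AE occurred in the double-blind study, so in the OLE it is medical history.
- Protocol 9.5.1: a TEAE of this study, counted overall but in none of the by-period tables.
- SAP 7.1.1: not decided.

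The synopsis and 6.4.2.2 together put the AE in neither study's summary. Section 9.5.1, or the SAP read without a carve-out, puts it in this study's summary under the randomized arm.

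**4. Effect of keeping it under two groups.** Maintenance doses in the active arm are 36, 45 or 54 mg/day, so moving up to reach 36 mg/day most naturally describes placebo subjects. This is an inference, because Figure 1 is not visible in the text available. For one arm, let *p* be the proportion of subjects with a given TEAE before conversion, *f* the share of the remaining subjects who convert, and *q* the probability of a first such AE during conversion. The table then shows

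p + (1 − p) × f × q.

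With A for SPN-810 and P for placebo, and compared with a table closed before conversion, the difference SPN-810 minus placebo changes by

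(1 − p_A) f_A q_A − (1 − p_P) f_P q_P.

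For an AE that the drug causes early, q_P should exceed q_A, because one arm is starting the drug and the other is already on it. The change is then negative and the contrast narrows. The documents give no values for *p*, *f* or *q*, so no size can be attached.

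**5. How many subjects.** Protocol 9.3 plans 186 randomized 1:1 with about 20% dropout: 186 × 0.80 = 148.8 completers, and 148.8 / 2 = 74.4 per arm. About 74 placebo subjects is thus the planned-size ceiling among completers, assuming equal dropout and that every completer enters the OLE. SAP 5.1 says that the study was halted, so the actual number is not known from the documents.

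**The case against.** The strongest reply is that only the synopsis sentence is out of line. Sections 6.4.2.2 and 9.5.1 fit together: an AE during conversion can be a TEAE of 810P503 and also be carried into the OLE as history. Since the SAP supersedes the protocol's methods and has no carve-out, the natural reading counts these AEs in 810P503. The summary of changes records that the visit number in 6.4.2.2 was altered, so the synopsis may simply have kept an older cut-off. This stands: there are two competing rules, not three, and omission is a risk rather than a certainty. It does not close the point, because SAP 7.1.1 never states the window.

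A reader might infer that these AEs disappear from the safety database. The documents do not support that. AEs are recorded at Visit 8 for all subjects (Table 1, 5.3.8), SAP 5.1 lists all data, and SAP 7.1.5 lists AEs by subject. The gap is in the summary tables.

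A reader might also infer that extrapyramidal events are lost. They have a separate special-interest route (protocol 6.4.3.2), SAP 7.1.5 tabulates them with no Visit 7 cut-off, and the movement scales are given at Visit 8 and summarized under SAP 7.6. That answers omission. It does not answer attribution, since SAP 7.1.5 provides no split for conversion.

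The Visit 8 start in 6.4.2.2 can also be read another way: it could mean asking at Visit 8 about events since Visit 7. The medical-history sentence weighs against this. Finally, 810P304's own plan may capture these AEs; it is not available to check.

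**Conclusion.** The concern holds as a defect in how AEs are assigned and summarized, not in how they are collected. For extension enrollees, current protocol texts disagree about AEs with onset on Days 36 to 45, and the SAP does not settle which applies. Each route has a cost. The synopsis with 6.4.2.2 may leave these AEs out of both studies' summary tables. Section 9.5.1 with the SAP's two groups would count AEs from former placebo subjects' first active exposure as placebo events and so tend to narrow the safety contrast.

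The second consequence rests on the inference that the conversion card starts placebo subjects on SPN-810. The first depends on an OLE plan that is not available. The interval is 10 of 45 dosed days. The number of subjects is unknown, and the ceiling of about 74 should not be read as an estimate for a halted study. The efficacy endpoints are not affected.

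**What to change.** - In SAP 7.1.1, state that AEs with onset from first dose through Visit 8 are summarized in 810P503. Keep the synopsis window of 7 days after last dose for subjects who do not enter the OLE.
- Limit the main between-arm TEAE table to onsets before the first conversion or taper dose.
- Show later onsets in a separate Conversion/Taper table by randomized arm and treatment actually received. Identify special-interest events there, so that SAP 7.1.5 follows the same split.
- Record in the SAP that this supersedes the synopsis sentence, and reconcile the synopsis with protocol 6.4.2.2 and 9.5.1.

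The cost is SAP wording and one extra table. The AEs are already recorded at Visit 8, so no new AE collection is needed. The split needs the date of the first conversion or taper dose; if that date was not captured, the date the card was dispensed would serve.
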